The assessments are itemized below. In addition, participants will be asked to complete practice notes throughout their intervention.

Administered at Baseline: 3RP Battery of questionnaires Hair Cortisol Samples

Administered 3 months post enrollment:

3RP Battery of questionnaires Hair Cortisol Samples Participant Feedback Questionnaire

Administered during Intervention (either starting after baseline or 3 months post enrollment)

Progress Note

Administered 6 months post enrollment

3RP Battery of questionnaires Participant Feedback Questionnaire

Intervention

In the SMART-3RP intervention, sessions focus on developing an understanding of stress physiology and the physiology of the relaxation response (RR), on developing a regular practice of eliciting the RR, and on learning cognitive behavioral and positive psychology/resilience skills. In addition to the weekly group sessions, participants will receive audio recorded guided meditations for independent relaxation practice. Participants are expected to practice eliciting the RR for approximately 20 minutes a day throughout the course of the study, using the audio recording provided and/or any other meditative or mind body techniques. Participants will complete a daily log reporting how often and by which methods they are practicing the RR. (Please see attached practice log).

The SMART-3RP will be delivered virtually, via the Partner's secure videoconferencing platform. The intervention will not be delivered clinically, and will be a psycho-educational intervention. Participants will be asked to wear headphones and sit in a quiet room by themselves for each of the sessions.

What does it involve?

The SMART-3RP involves participating in eight, 1-1.5 hour sessions, once a week via videconferencing. The SMART-3RP is a manualized psychoeducational program and each participant will be sent a manual to use during each session and to practice exercises each week. In each session, participants will learn a new type of relaxation response method, such as meditation or seated yoga. Participants will also learn more about stress and its effects on the body and mind. The program will discuss strategies and techniques to help participants manage daily stressors, through the use of breathing techniques, and cognitive reappraisal. We will also discuss adaptive strategies, such as incorporating more positive activities into participant's lives to add enjoyment and time for self care.

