Groups consist of no more than 8 participants, and can be smaller as well. The group consists of participants, parents of children with ASD, as well as a group leader and a study staff member. The study staff member is fully trained in observing SMART-3RP groups, and will be setting up the videoconferencing group each week, and helping participants connect to the group.

At the start of the program, the leader clearly discusses the importance of confidentiality and asks that participants sit in a room alone, not record the sessions, and not share any other group members' personal information with others outside of the group. The program also discusses goal setting to help partcipants identify some personal goals and strategize ways to begin tackling them. These goals are addressed through weekly practice.

Homework and exercises

Homework each week involves practicing the skills discussed in the previous session. Participants are encouraged to listen to the audio recordings of meditation exercises that come with the program manual. In each session, participants are encouraged to discuss their thoughts about their practice, what they liked, and what they did not like. No one is required to do any practice that they do not find helpful. We collect copies of the practice logs. The practice logs include:

- a) Types of RR exercises practiced and duration of practice
- b) Appreciations: participants are asked to list three things they appreciated each day of the week—this exercise helps bring awareness to the positive aspects of our lives, and allows us to re-live enjoyable moments through remembering them
- c) SMART goals—participants are encouraged to write down specific small goals for the week such as, "take a walk outside at least twice"—to help them moved towards their larger goals

Other exercises that we practice in the SMART-3RP include exercises that help participants identify specific stressors, how they feel when they experience stress, what types of thoughts they have, and what it is about the particular incident that makes them feel stressed. We do a practice exercise as a group and encourage participants to practice for homework by thinking about their thoughts and feelings when they get stressed. They are also encouraged to complete a coping log if they are interested. They do not turn this into us as it is just for their own benefit.

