The process of developing the Benson-Henry Institute's SMART-3RP is further described in [name] article, The Development of a Patient-Centered Program Based on the Relaxation Response: The Relaxation Response Resiliency Program (3RP). The current program that will be used in this study is an adapted version of the original program, and is tailored to the needs of parents of children with ASD.

Differences in the adapted program include:

-Examples in each exercise tailored to parents

-An introduction at the beginning of the program about parental stress, and how we hope to provide useful stress management skills to help parents of children with ASD.

-A list of recommended resources for parents if they are interested (list serves etc)

Participants randomized to Immediate or Waitlist will participate in the SMART-3RP program. Participants in the Immediate arm will be encouraged to practice the skills taught in the program

during the 3 month follow up period after completion of the 8 session SMART-3RP. Participants in the Waitlist arm will wait for approximately 3 months before beginning the SMART-3RP.

Participants in both groups will be given questionnaires at the same timepoints (baseline, 3 month post enrollment, and 6 month post enrollment). Study staff will email these questionnaires to the participants via the REDCap system. Participants who have not responded within two weeks of each time point will be contacted by telephone to ensure receipt of study data.

Figure 1 (below) illustrates the administration of questionnaires in both groups.

Figure 1. Study Design.

Remuneration

Participants will be given a \$20 gift certificate for completing 3 mo. survey and another \$20 gift certificate for completing the 6 mo. survey assessment.

Participants may also be compensated up to \$40 for their hair samples (\$20 for the first and \$20 for the second). Compensation will be provided for those who have already submitted at least their baseline hair sample, and for all future participants interested in completing their hair samples.

VI. BIOSTATISTIC ANALYSIS

We plan to conduct a pilot trial of a virtual-based SMART-3RP intervention for parents of children with ASD. Participants in this trial will be randomized to one of two groups: 1) Immediate SMART-3RP intervention, or 2) Waitlist control SMART-3RP group (starting approximately 3 months after enrollment).

The following questions will be assessed:

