REDCap (Research Electronic Data Capture) is a free, secure, HIPAA compliant web-based application hosted by the Partners HealthCare Research Computing Enterprise Research Infrastructure & Services (ERIS) group. The system offers easy data manipulation with audit trails, reports for monitoring and querying participant records, and an automated export mechanism to common statistical packages (SPSS, SAS, Stata, R/S-Plus).

Data will be stored on password protected computers that will be stored in secure locations at all times. Paper data files (with coded subject identification) will be stored in a locked filing cabinet. Only research staff will have access to these data locations.

A unique anonymous identifier will be assigned to each subject; subsequently, all data collected will be associated exclusively with this identifier. This includes all questionnaires administered over the course of the study, as well as home practice logs.

Data Management and Quality Control Procedures

To maximize accuracy and security, all survey data will be collected and stored on REDCap. Research staff will ensure that proper consent has been obtained before sending the REDCap survey to each participant.

Data and Safety Monitoring Plan

Adverse Event Monitoring: Throughout the study subjects will be monitored for the occurrence of events defined as any undesirable experience or unanticipated risk. Lack of effect of treatment is not considered an event. All adverse events will be reported on an adverse event form.

The principal investigator is ultimately responsible for data and safety monitoring. If study staff becomes aware of any adverse events, the event will be reported immediately to the Principal Investigator. The Principal Investigator has the responsibility of reporting serious adverse events (death, life threatening illness or injury, serious injury, or permanent disability) to PHRC within 72 hours of notification.

Subject Safety

In the case that an issue related to mandatory reporting or duty to warn arises, we will contact the Office of General Council for advice on how to proceed.

X. REFERENCES

⁴ Rivard, M., Terroux, A., Parent-Boursier, C., & Mercier, C. (2014). Determinants of stress in parents of children with autism spectrum disorders. Journal of Autism and Developmental Disorders, 44(7), 1609-1620.

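### Adverse event monitoring is promised for all participants, but no method of asking is stated and staff contact differs sharply by arm, so comparability of any by-arm harm summary is not assured

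*Protocol*

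**What the plan says.** The Data and Safety Monitoring Plan in Protocol section IX covers every participant: "Throughout the study subjects will be monitored for the occurrence of events defined as any undesirable experience or unanticipated risk." It adds: "All adverse events will be reported on an adverse event form." It then deals with escalation: "If study staff becomes aware of any adverse events, the event will be reported immediately to the Principal Investigator." It names no question, no schedule and no person responsible for asking.

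The assessments itemised in section V are the questionnaire battery, hair samples, a feedback questionnaire and a progress note. No adverse event instrument is among them, and the progress note is used only while a participant is in the programme.

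On contact with staff, section V says of the programme: "The SMART-3RP involves participating in eight, 1-1.5 hour sessions, once a week via videconferencing." On who attends: "The group consists of participants, parents of children with ASD, as well as a group leader and a study staff member." For the control arm: "Participants in the Waitlist arm will wait for approximately 3 months before beginning the SMART-3RP." Both arms share the survey schedule, "Participants in both groups will be given questionnaires at the same timepoints (baseline, 3 month post enrollment, and 6 month post enrollment", and the surveys go out remotely: "Study staff will email these questionnaires to the participants via the REDCap system." A telephone call follows only if a survey is still missing after two weeks, and its purpose is to obtain the data.

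Neither Protocol section VI nor the SAP mentions adverse events.

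**The concern.** In a waitlist design the arms differ by construction in how often they meet staff. If events are not asked about at fixed times in the same way, the number recorded depends partly on how many chances a parent has to mention one. Section I describes a population with high distress and depressive symptoms, so background events are plausible in both arms.

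Any safety summary of this pilot would be read with a national programme in view, which section I gives as the ultimate objective. Closer contact could make the programme look worse than waiting. A real excess could also be explained away as closer contact, and events in either arm's session-free months could go unseen. Events that nobody asked about cannot be recovered at analysis.

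**Working it through.** The documents give no event rate, detection rate or safety analysis, so there is no stated figure to reproduce. The contact counts below come from the documents; everything after them rests on assumptions.

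**Step 1. Scheduled contacts per participant** (section V; consent, any software test call and baseline excluded)

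| Period | Immediate | Waitlist |
|---|---|---|
| After baseline, up to and including 3 months | 8 sessions + 1 survey = 9 | 0 sessions + 1 survey = 1 |
| After 3 months, up to and including 6 months | 0 sessions + 1 survey = 1 | 8 sessions + 1 survey = 9 |

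The sessions fill about 8 of the roughly 13 weeks in a period. During them the attending arm also completes a weekly practice note, which the Session 1 outline says includes a symptom check.

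**Step 2. Arm size.** About 70 participants (section III) randomised 1:1 (section IV): 70 / 2 = 35 per arm.

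**Step 3. What unequal detection would do.** Expected recorded events = n × true risk × probability of detection. With equal true risk in both arms, n and the risk cancel, and the apparent risk ratio is the ratio of the detection probabilities. Assume a true risk of 20%: 35 × 0.20 = 7 true events per arm.

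| Assumed detection, Immediate vs Waitlist | Recorded to 3 months | Apparent ratio |
|---|---|---|
| 0.9 vs 0.9 | 6.3 vs 6.3 | 1.0 |
| 0.6 vs 0.4 | 4.2 vs 2.8 | 1.5 |
| 0.9 vs 0.6 | 6.3 vs 4.2 | 1.5 |
| 0.9 vs 0.3 | 6.3 vs 2.1 | 3.0 |
| 0.8 vs 0.2 | 5.6 vs 1.4 | 4.0 |

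**Step 4. Tying detection to the contact counts.** Suppose each contact independently reveals an event with probability q. Detection is then 1 − (1 − q)^9 with nine contacts and q with one.

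- q = 0.1: 0.613 vs 0.100, ratio 6.1
- q = 0.2: 0.866 vs 0.200, ratio 4.3
- q = 0.3: 0.960 vs 0.300, ratio 3.2

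This model is crude. It lets every contact reveal every event, although an event late in the programme has few contacts left, and that inflates the ratio. It also treats an emailed survey with no named event question as equal to a live session, and that deflates it.

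**Step 5. After the fix.** If both arms are asked the same questions at the same times and detection is equal (0.9 assumed), the record is 35 × 0.20 × 0.9 = 6.3 in each arm, ratio 1.0.

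**The case against.** Several stronger readings are tempting, and the documents do not support them.

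- *Events are recorded only if staff happen to notice them.* A reader might infer this from the sentence on staff awareness. That sentence sets when an event goes to the Principal Investigator. The same section commits to monitoring everyone and to putting every event on a form. The gap is an unstated method, not an awareness-only rule.
- *Monitoring is absent in the session-free months.* The documents are silent on how it is done; they do not show that it is not done.
- *The control arm is useless for harms and the programme will look several times more harmful.* No between-arm adverse event comparison is planned, so no planned estimate or test is affected. The ratios follow entirely from the detection rates chosen.
- *Nothing asks about events.* The assessment list names instruments, not items. The practice log and feedback questionnaire are attachments outside the public text, and the feedback questionnaire is listed at both 3 and 6 months without restriction to one arm. An event item cannot be ruled out.

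Three further points have weight. Both arms complete the same visual analogue scales for distress and physical discomfort, so average worsening would show in the planned comparison. These are efficacy outcomes, however, and nothing links a score to the event form. The symptom check is described as homework. It is missing from the list of collected log contents in section V, and no text says staff screen it for events, so it adds little certain capture. Lastly, this is a small psycho-educational pilot with modest stated risks, and some of them (group confidentiality, practice burden) arise mainly during attendance. That lowers the urgency; it does not supply a method of asking.

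**Conclusion.** The point holds as a gap in method. Monitoring is promised throughout, no way of asking is stated, and scheduled contact is 9 against 1 up to 3 months, reversing afterwards. If detection rises with contact, recorded events will cluster in the attending arm, so comparability of a by-arm harm summary is not assured.

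Only the contact counts are established. The size of any distortion is unknown: the assumed inputs give false ratios from 1.0 (equal detection) to 6.1 (nine contacts against one, each with a 10% chance of revealing an event). The conclusion also assumes that no attached form already asks both arms about events. It leaves the planned efficacy and cortisol analyses untouched. It is a cheap improvement worth making, not a flaw that undermines the trial.

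**What to change.** First check the attached forms. If one already asks both arms about adverse events at 3 and 6 months, cite it in the Data and Safety Monitoring Plan and no new items are needed.

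Otherwise:

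- Add one identical short question set to the 3- and 6-month REDCap surveys in both arms: any new or worsened emotional or physical problem since the last survey, any hospital stay, any privacy problem.
- Flag positive answers to staff for the existing adverse event form.
- Summarise events by arm and period (baseline to 3 months, 3 to 6 months) from these questions, with the number who answered as the denominator.
- List events volunteered in sessions separately.

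The cost is an amendment, a few survey items, about a minute more per survey and more minor events to log. No new visits or staff are needed. The cure is partial: parents know their arm, and the programme trains attention to bodily and stress signals, so reporting may still differ under identical questions.

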Official Title of Study: Evaluation of a resiliency intervention for parents of children with Autism Spectrum Disorder (ASD)

NCT number: NCT02995408

Date of document: 9/14/16

ASD Study Aims							
Туре	Specific Aim	Hypothesis	Measure	Statistical Test Type			
Primary	To develop and determine the feasibility and acceptibility of an 8-session Relaxation Response Resiliency program for parents of children with ASD	The SMART-3RP virtual delivery will be feasible to implement and acceptable to parents of children with ASD.	
 
assessing the number of sessions attended
 
adherence to Relaxation Response Practice
 
Participant Feedback Survey
 
				
Primary	To test the effectiveness of a pilot waitlist controlled trial on improving resiliency and on improving stress reactivity, growth enhancement, and parental stress	Patients randomized to the Immediate group will report significantly greater scores on the primary outcomes and on the secondary outcomes at 3 mo. post enrollment	
 
General Self-Efficacy Questionnaire (GSE)
 
Current Experiences Scale (CES)
 
Visual Analogue 0-10 scales (stress, distress, coping, and physical discomfort) (VAS)
 
Measure of Current Status-A (MOCS)
 
Cognitive and Affective Mindfulness Scale-Revised (CAMS-R)
 
Parental Stress Scale (PSS)
 
Baseline-3 mo. scores on primary and secondary outcome measures between the Immediate and waitlist control group
 
	
 
paired samples t-tests to compare within group differences from 3 mo. to baseline
 
independent samples t-tests to compare the difference between the Immediate group's 3 months post enrollment and baseline assessment results
 
			

	ASD Study Aims							
Туре	Specific Aim	Hypothesis	Measure	Statistical Test Type				
Secondary	to investigate the extent of pre-post changes in primary and secondary outcomes among participants randomized to both conditions	Scores on primary and secondary outcome measures will improve from pre-post intervention.	• Immediate: assessments from baseline-3 mo.; Waitlist: from 3-6 mo.)	• paired samples t-tests to compare all primary and secondary assessments from pre-post SMART 3-RP				
